2.2. Specific goals

- a. - Estimating Hyperkalaemia prevalence in these patients.
- b. - Assessing the role of hyperkalaemia with the use of non-optimal therapy doses.
- c. - Estimating 12 months hyperkalaemia incidence on these patients and describing the severity of the episodes.
- d. - Estimating incidence of HF hospital admission and/or death in these patients on a medium term basis (12 months) and its association with existence of hyperkalaemia during follow up.
- e. - Assessing hyperkalaemia risk during follow-up in relation with the existence of diabetes and/or renal failure (RF) at baseline visit.

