5. Not having completed HF drug titration stage at the moment of inclusion (this stage is not completed if, on doctor's judgement, possible maximum doses have not been reached in RAA system drugs and any of these drugs has been included or dose-modified in recruitment visit)
6. Informed consent refusal

At any time during follow-up patients can leave the study (and will be censored in the analysis) or retire their consent (and will be excluded from the analysis).

3. 2. Considerations about simple size

Assuming a 10% risk of outcomes (mortality or HF hospital admission) among the exposed (hyperkalaemia), 2.5% among the non-exposed and a 7:1 non-exposed/exposed ratio, 73 exposed and 511 non-exposed patients should be included to have a 80% power to detect these differences with a 95% confidence level. The recruitment goal is set at 600 patients.

This sample size allows a precision of $\pm 2,4\%$, assuming a prevalence of hyperkalaemia at baseline of 10% and with a 95% confidence level. Furthermore, assuming 5% hyperkalaemia cumulative incidence through follow-up among hyperkalaemia-free patients at baseline, the proposed sample size, allows a precision of $\pm 1,8\%$ with a 95% confidence level.

3. 3. Selection of centres

The number of participant centres throughout Spain will be 20 and a cardiologist will be the principal investigator at every centre. The centres have been selected either among those with excellence-certified HF units, included in CiberCV Consortium or

with good performance in previous similar registries; this selection is not random, but based on interest and high performance criteria in the field of HF.

3. 4.- Source of information

Data will be obtained directly from the participants at the planned visits and completed with the review of their medical records if needed.

3. 5. Variables and CRF (appendix 1)

The main outcome variables are:

a.- Hyperkalaemia. Serum Potassium (K^+) will be measured in baseline and follow-up visits, but also if there is any intermediate hospital admission. All available potassium measurements during follow-up will be reviewed and values of hyperkalaemia identified. Hyperkalaemia will be considered with (K^+) Values $> 5,4$ mEq/L

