b.- Proportion of patients using drugs with proven efficacy for HF with REF -but also linked with hyperkalaemia- (ACEIs/ARB-II/ARNI and MRAs) and proportion of patients with use of optimal doses (based on current ESC heart failure guidelines²) of the same drugs; reason for not using them (or not receiving optimal doses) will be registered.

Proportion of patients in the following categories will also be computed:

- No ACEi/ARB/ARNI or at less than target dose and no MRA
- ACEi/ARB/ARNI at target dose and no MRA
- ACEi/ARB/ARNI at target dose and MRA at less than target dose
- ACEi/ARB/ARNI at target dose and MRA at target dose

c.- Hospital admissions during follow-up and main cause for them. Outcomes considered will include HF admissions caused by hyperkalaemia and related events. Outcome Serum (K^+) values will be also registered.

d.- Mortality and cause.

HF (and hyperkalaemia) hospital admissions and mortality will be independently considered as outcomes; joint outcome incidence of both will be also calculated.

The remaining variables are set out in appendix 1. The most important variables are defined in section 4.

3. 6. Study development

Every participating centre will include from inclusion date (as described in section 3.1) the first 30 heart failure outpatients who fulfil the inclusion criteria and none of the exclusion ones. The excluded patients will be also registered, pointing out the reason of exclusion. The data to be collected during the initial visit will include the variables described in Appendix 1: demographic, clinical, blood sample test, and functional. A follow-up and final visit will be scheduled after 12 months for collecting all the variables the study requires (Appendix 1). Hospitalisation data since inclusion visit will be also collected, together with the information of blood sample test performed in such period for detecting hyperkalaemia episodes. Mortality data will include date and cause, where possible. If follow-up visit cannot be conducted, the reason for it will be registered. The collection and management of data is described in section 5. The envisaged length of the study is 24 months since approval date.

3. 7. Limitations

Mild elevations of serum potassium that do not lead to hospital admission between planned visits may go unnoticed.

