6. PLAN FOR DATA ANALYSIS

Hyperkalaemia prevalence at basal visit and the rate of patients who do not receive and/or reach optimal doses of drugs of interest (ACIEs, ARB-II, MRAs) will be estimated and their corresponding 95% confidence intervals computed. The reason for not receiving and/or reaching optimal doses of drugs will be described, especially if it is due to hyperkalaemia.

For those patients who do not present hyperkalaemia at baseline, 12 month hyperkalaemia cumulative incidence (95% confidence interval) will be estimated; also it will be estimated the proportion of patients who have to modify their therapy due to hyperkalaemia.

The number of episodes of hyperkalaemia during follow-up in relation to the number of patients will be estimated and their severity and the therapy changes that induced described. Also 12 months cumulative incidence of clinical outcomes will be estimated: hospitalisation due to HF or to, hyperkalaemia (and related events) and mortality, considered as individual and composite outcomes. The association between hyperkalaemia and occurrence of outcomes will be analysed and also adjusted using potential confounding factors by means of logistic regression models

The quantitative variables will be generally described using either the mean and the standard deviation or the median and interquartile range according them following or not a normal distribution. When comparing groups, t-student test will be used for continuous variables and chi-square test for qualitative ones.

Both, intermediate and final analysis, are planned to be carried out after baseline-visit closure and at the end of follow up (12 months).

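### Admissions for hyperkalaemia count as outcome events in the composite that is then related to hyperkalaemia during follow-up, so that association is inflated by definition

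*Protocol*

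**What the plan says.** **Exposure.** Specific goal d (Section 2.2) asks about the clinical outcomes and "its association with existence of hyperkalaemia during follow up". Sections 3.5 and 4 define hyperkalaemia as serum potassium above 5.4 mEq/L. Section 3.5 takes potassium at the two visits and at any hospital admission in between, and reviews every available follow-up value.

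**Outcomes, wider version.** Section 6 plans the 12-month cumulative incidence of "hospitalisation due to HF or to, hyperkalaemia (and related events) and mortality, considered as individual and composite outcomes". Section 3.5 is in line with this: "HF (and hyperkalaemia) hospital admissions and mortality will be independently considered as outcomes; joint outcome incidence of both will be also calculated". Item c of the same section adds: "Outcomes considered will include HF admissions caused by hyperkalaemia and related events".

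**Outcomes, narrower version.** The first part of goal d reads "Estimating incidence of HF hospital admission and/or death in these patients on a medium term basis (12 months"). The sample size in Section 3.2 starts from "Assuming a 10% risk of outcomes (mortality or HF hospital admission) among the exposed (hyperkalaemia"). Neither includes admissions for hyperkalaemia.

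**Analysis.** Directly after its list of outcomes, Section 6 states: "The association between hyperkalaemia and occurrence of outcomes will be analysed". Adjustment is by logistic regression. The sentence names no other set of outcomes and leaves none out. Nothing in the protocol requires the exposure to come before the outcome.

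**The concern.** An admission caused by hyperkalaemia during follow-up meets the exposure definition and the outcome definition at once. In the unexposed group such an admission cannot occur, because it would move the patient into the exposed group. The composite, and any admission outcome that pools the two causes, therefore collects extra events on one side only. Adjusting for confounders does not remove an overlap of definitions.

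Taken as an individual outcome, admission for hyperkalaemia has no events among the unexposed, so its odds ratio cannot be estimated.

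What is at stake is goal d. It asks whether hyperkalaemia carries a worse prognosis for HF admission and death. A positive result for the composite could appear when hyperkalaemia has no relation to either, and the result alone would not show which had happened.

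**Working it through.** **1. The protocol's own figure.** Inputs from Section 3.2: risk 10% in the exposed and 2.5% in the non-exposed, ratio 7:1, 80% power, 95% confidence. The check uses the two-sided comparison of two proportions with pooled variance and no continuity correction:

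- pooled risk = (0.10 + 7 × 0.025)/8 = 0.0344
- n exposed = [1.96 × √((1 + 1/7) × 0.0344 × 0.9656) + 0.842 × √(0.10 × 0.90 + 0.025 × 0.975/7)]² / 0.075² = 72.6, rounded up to 73
- n non-exposed = 7 × 73 = 511

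This reproduces the stated 73 and 511, with power 80.2%. The planned odds ratio is (0.10/0.90)/(0.025/0.975) = 4.33. The calculation is for mortality or HF admission, not for the wider composite.

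**2. Effect of the overlap when there is no true association.** Let p0 be the risk of HF admission or death, equal in both groups. Let k be the expected number of the 73 exposed who are admitted for hyperkalaemia, taken as independent of the other events. The non-exposed have none by definition. Then:

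- composite risk in the exposed: p1 = 1 − (1 − p0)(1 − k/73)
- composite risk in the non-exposed: p0
- OR = [p1/(1 − p1)]/[p0/(1 − p0)]

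Example with p0 = 0.025 and k = 3: p1 = 1 − 0.975 × (70/73) = 0.0651, and OR = (0.0651/0.9349)/(0.025/0.975) = 2.71.

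The values of k are assumptions, because the protocol gives no rate: 1, 3 and 5 of 73 are 1.4%, 4.1% and 6.8%. Of the base risks, 2.5% is the protocol's, and 5% and 10% are assumed. The last column is the probability of two-sided p<0.05 for the unadjusted, uncorrected chi-square test, by exact enumeration over Binomial(73, p1) and Binomial(511, p0).

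| p0 | k | p1 | OR | Chance of p<0.05 |
|---|---|---|---|---|
| 2.5% | 0 | 0.0250 | 1.00 | 4.0% |
| 2.5% | 1 | 0.0384 | 1.56 | 14.1% |
| 2.5% | 3 | 0.0651 | 2.71 | 46.7% |
| 2.5% | 5 | 0.0918 | 3.94 | 75.6% |
| 5% | 0 | 0.0500 | 1.00 | 4.6% |
| 5% | 1 | 0.0630 | 1.28 | 9.5% |
| 5% | 3 | 0.0890 | 1.86 | 30.2% |
| 5% | 5 | 0.1151 | 2.47 | 56.8% |
| 10% | 0 | 0.1000 | 1.00 | 4.9% |
| 10% | 1 | 0.1123 | 1.14 | 7.3% |
| 10% | 3 | 0.1370 | 1.43 | 18.7% |
| 10% | 5 | 0.1616 | 1.74 | 36.9% |

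**3. Overlap that alone reproduces the planned effect.** At p0 = 2.5%, p1 reaches 10% when k/73 = 1 − 0.90/0.975 = 7.7%, which is 0.077 × 73 = 5.6 patients. Between 5 and 6 hyperkalaemia admissions among the exposed would then mimic the whole planned difference.

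**4. With hyperkalaemia admissions left out.** The composite is HF admission or death. The no-effect odds ratio returns to 1.00, and 73/511 remains the right calculation for it.

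**The case against.** The strongest reply is that the circular analysis may not be intended.

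- **Composite for incidence only.** Sections 3.5 and 6 introduce the wider composite for incidence, which is descriptive. Where the protocol spells out the outcome and exposure of the association together (goal d, Section 3.2), the outcome is HF admission or death. This reading is possible. But Section 6 lists the outcomes and then, in the next sentence, relates hyperkalaemia to the outcomes without naming another set. The plain reading is the list just given.
- **Exposure timing.** That sentence gives no time window, and with baseline hyperkalaemia as the exposure the overlap would not be definitional. That is correct as a limit, but goal d says follow-up.
- **The main goal is broader.** Section 2.1 speaks of hospital admission without restricting it to HF, so hyperkalaemia admissions fit there. This supports reporting them. It does not make them a valid outcome for an exposure that they define.
- **Components are also reported singly.** A composite driven by hyperkalaemia admissions might be noticed beside HF admission and mortality. This softens the harm but does not make the composite interpretable.
- **Size.** The large figures need 4% to 7% of exposed patients admitted for hyperkalaemia at the lowest base risk, and they are unadjusted. With one such admission the odds ratio is 1.14 to 1.56. This stands, and is why a range is shown.
- **Testing at admission.** Potassium is measured at every admission, so an HF admission itself creates a chance of being classed as exposed. This is a separate detection problem. It can also touch HF admission analysed alone, and removing the definitional overlap does not cure it.

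**Conclusion.** The point holds and should be fixed. As written, Section 6 with goal d relates hyperkalaemia during follow-up to a composite that contains admissions for hyperkalaemia. The bias is upward as soon as one exposed patient has such an admission as the only composite event.

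Its size is uncertain. In the scenarios shown, the no-effect odds ratio runs from 1.14 to 3.94 and the chance of a false p<0.05 from 7% to 76%. It is modest if hyperkalaemia admissions are rare or the base risk is high, and comes near the planned 4.33 only at the protocol's own 2.5% base risk. These figures assume group sizes of 73 and 511, independence of the event types, and no adjustment.

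Mortality alone and HF admission classified by cause are free of the definitional overlap. Events under the undefined label of related events need not be circular, since some may occur without raised potassium. Apart from the bias, the outcome in Sections 3.5 and 6 differs from that in goal d and Section 3.2, and the protocol does not say which one the association uses.

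**What to change.** - In Sections 3.5 and 6, state that the outcome of the association analysis is HF admission and/or death, as in goal d and Section 3.2.
- Classify each admission by its recorded main cause: HF stays in the outcome, hyperkalaemia is left out. Reword the phrase in Section 3.5 c that treats hyperkalaemia as a cause of HF admissions, because it blurs the two.
- Say which events count as related events.
- Report hyperkalaemia admissions descriptively under goal c, as part of the severity of episodes. Label any composite that includes them as descriptive only.

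The cost is wording. Section 3.5 c already collects the main cause of each admission, and the 73/511 sample size stands because it was computed for the narrower outcome. The only loss is slightly fewer composite events.

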3. STUDY DESIGN

National multicentric prospective observational study that includes 12 months follow-up of consecutive cases of HF outpatients with REF. Inclusion baseline visit and follow-up visit at 12 months will be scheduled for collecting clinical and blood sample data of patients indicated later on in this protocol.

The study will be performed in ordinary conditions of clinical practice; no additional procedures or interventions will be performed. Patients will be selected in cardiology outpatient clinics of 20 Spanish centres, including the first 30 patients meeting inclusion and exclusion criteria. All patients will undergo the common studies according to usual clinical practice and at least both, potassium and renal creatinine clearance values will be collected.

To respond to the main objective, prevalence of hyperkalaemia (as defined later in the protocol) at baseline will be determined as well as the appearance of new hyperkalaemia cases in the follow up of patients that had normal potassium levels at baseline visit; their relationship with outcomes of interest will also be determined.

Variables to be collected at each visit are indicated in appendix 1.

3. 1. Definition of the study population and selection criteria

The study population is composed of HF outpatients with REF from excellence Spanish centres.

The study will be performed in 20 Spanish centres, either SEC HF- excellence certified, integrating official research networks or with excellent performance proven in previous similar initiatives (relation of centres and researchers in Appendix 2).

Every centre will include the first 30 consecutive cardiology outpatients who fulfil the inclusion criteria and that do not present any exclusion criteria. All pre-screened patients will be indicated, together with the reason of their exemption if occurs.

Inclusion criteria

1. Patients, women or men, aged 18 or more
2. Documented HF with REF (<40%) diagnosis
3. Signed written informed consent

Exclusion criteria

1. Any type of disorder affecting the capacity to give free and informed written consent
2. Clinical trial enrolment at the moment of the inclusion
3. Patients suffering stage 5 chronic kidney disease
4. Patients with less than a year life span due to diseases different from HF

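### Section 6 names only logistic regression and does not require hyperkalaemia to precede the outcome, so goal d's odds ratio can be biased even if hyperkalaemia has no effect

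*Protocol*

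**What the plan says.** Section 2.2, goal d, asks for the 12-month incidence of HF admission and/or death and "its association with existence of hyperkalaemia during follow up". Section 3 refers to "appearance of new hyperkalaemia cases in the follow up of patients that had normal potassium levels at baseline visit; their relationship with outcomes of interest", having just named baseline prevalence as well, so the exposure could be new-onset hyperkalaemia alone or baseline and new-onset cases together. Section 6 says only hyperkalaemia, and names one model: "The association between hyperkalaemia and occurrence of outcomes will be analysed and also adjusted using potential confounding factors by means of logistic regression models".

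Three other statements bear on timing and measurement:

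- Section 3.5 says that potassium "will be measured in baseline and follow-up visits, but also if there is any intermediate hospital admission". It adds that every potassium value available from the follow-up period will be reviewed, and Section 3.6 says that blood tests from that period are collected.
- Section 3.7 concedes that small rises between visits may be missed when the patient is not admitted.
- Section 3.1 says: "At any time during follow-up patients can leave the study (and will be censored in the analysis").

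Section 3.2 sizes the study for this association with a 10% outcome risk in the exposed and "2.5% among the non-exposed and a 7:1 non-exposed/exposed ratio, 73 exposed and 511 non-exposed patients should be included".

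**The concern.** A logistic model with one record per patient treats exposure as fixed before the outcome. Hyperkalaemia during follow-up is not fixed in that way, and two mechanisms act in opposite directions.

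- **Down.** A patient who dies early has less time in which to be recorded as hyperkalaemic, so deaths collect among the never-exposed.
- **Up.** An HF admission is itself an occasion for a potassium test, while rises in patients who are not admitted can be missed. Having the outcome raises the chance of being classed as exposed.

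Adjusting for baseline confounders removes neither, because the fault lies in the order and measurement of events. Prognosis is in the study title and is part of the main goal. At stake is whether the reported association can be told apart from an artefact of timing.

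**Working it through.** **Reproducing the plan's own figure.** For 10% against 2.5%, ratio 7:1, two-sided 5%, 80% power, pooled-variance test without continuity correction, the formula gives 72.6, so 73 exposed and 511 non-exposed (power 80.2%). The sample-size arithmetic is sound.

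**Which exposure fits 73?** With 600 patients and 10% prevalence, 60 are exposed at baseline. Section 3.2 goes on, "assuming 5% hyperkalaemia cumulative incidence through follow-up among hyperkalaemia-free patients at baseline", which gives 540 × 0.05 = 27 new cases. Baseline plus new-onset is 87. The planned 73 is far closer to 60 or 87 than to 27, so the pooled reading leads here.

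**Inputs from the protocol.** Prevalence 10%; incidence 5%; overall outcome risk R = (10% + 7 × 2.5%)/8 = 3.44%.

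**Assumptions.** Hyperkalaemia has no effect; rates are constant and independent; d = share of outcomes that are deaths; a = share of outcome (index) admissions with potassium above 5.4 mEq/L. The protocol gives neither d nor a.

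**Formulas.**

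- Hazards per year: hyperkalaemia −ln(0.95) = 0.0513; outcome −ln(1 − 0.0344) = 0.0350.
- Probability of new-onset hyperkalaemia before death, given death within 12 months: 0.0251, against 0.05 in patients without the outcome.
- New-onset exposure in cases: c = d × 0.0251 + (1 − d) × [1 − 0.95 × (1 − a)].
- Pooled exposure: cases 0.10 + 0.90c; non-cases 0.10 + 0.90 × 0.05 = 0.145.

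Example, d = 0.3 and a = 0.10: c = 0.3 × 0.0251 + 0.7 × 0.145 = 0.109. Pooled exposure in cases is 0.198, and the odds ratio is (0.198/0.802)/(0.145/0.855) = 1.46.

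**Null odds ratios**

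| Deaths (d) | Index admissions hyperkalaemic (a) | Baseline + new-onset | New-onset only |
|---|---|---|---|
| 100% | not applicable | 0.82 | 0.49 |
| 50% | 0% | 0.91 | 0.74 |
| 50% | 2.5% | 1.00 | 0.99 |
| 50% | 5% | 1.08 | 1.24 |
| 50% | 10% | 1.26 | 1.77 |
| 30% | 0% | 0.95 | 0.84 |
| 30% | 5% | 1.19 | 1.56 |
| 30% | 10% | 1.46 | 2.32 |

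At d = 30% and a = 20%, an extreme case, the values are 2.05 and 4.04.

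**Allowing for other admissions.** Section 3.5 has potassium measured at any admission, so patients without the outcome who are admitted are tested too. If 20% of them are (an assumption) with the same positivity, their new-onset exposure at a = 10% becomes 0.8 × 0.05 + 0.2 × 0.145 = 0.069. The pooled 1.46 falls to 1.28 and the 1.26 falls to 1.11. The extreme 2.05 falls to 1.80, 1.59 or 1.42 if 10%, 20% or 30% are admitted.

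**Independent simulation, 4 million patients per scenario, no effect.** For mortality, new-onset ever/never coding gave 0.45 to 0.48, and pooling in baseline cases gave 0.82 to 0.84. Treating new-onset exposure as time-dependent on the mortality data gave rate ratios of 0.98 to 1.01. For non-fatal admission (10% admitted, 3% to 5% positive per test), one extra test at admission gave 2.03 to 2.06 when the only other test was at month 12. With three further routine tests for everyone it gave 1.27 to 1.29. A separate set of simulations with baseline exposure alone gave 1.00 to 1.03.

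**The case against.** The strongest reply is that Section 6 does not say ever/never, and does not say that its exposure is hyperkalaemia during follow-up. Coding and lag rules are often left to a statistical analysis plan, and pooled logistic regression by interval would satisfy the words used. This stands in part: the coding is inferred. But the protocol itself pairs a follow-up exposure with a single named model and sets no order of events, so this is a method poorly matched to its goal and not just a missing detail.

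Second, the upward bias is softened by tests at non-outcome admissions and by the review of all available potassium values. Both points stand; they shrink the bias without removing it.

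Third, a pooled bias of 0.82 to about 1.5 is small beside the planned contrast, an odds ratio of (0.10/0.90)/(0.025/0.975) = 4.33, and beside the sampling error. That is fair, and it limits the severity. It does not help in reading a modest observed association.

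A reader might infer that the odds ratio is certain to be wrong, or wrong by a factor of two to four. The documents do not support that. The biases can cancel, and the largest figures need a new-onset-only exposure that fits the 73 planned exposed poorly, high positivity at admission, or both.

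**Conclusion.** The concern holds as a risk of bias of unknown direction in one association. For baseline plus new-onset exposure, with up to 10% of index admissions hyperkalaemic, the null odds ratio runs from about 0.82 to about 1.5, or up to about 1.3 if 20% of non-cases are also admitted and tested. New-onset-only exposure gives 0.49 to 2.3 before that allowance. The existence of the problem follows from the text together with one-record ever/never coding. Its size rests on assumed death shares, positivity and admission rates.

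Two lesser notes. Ordinary logistic regression cannot censor leavers as Section 3.1 intends, but with 10% to 20% non-informative leavers the pooled effect is only about 1.01 to 1.03. Sections 3.5 and 6 also count hyperkalaemia admissions as outcomes, so exposure and outcome overlap there. A reader might extend this to goal d, but goal d's own endpoint is HF admission and/or death and does not include them.

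The prevalence and incidence estimates and the sample-size arithmetic are not in question. This should be fixed before the final analysis.

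**What to change.** In Section 6:

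1. For hyperkalaemia during follow-up, count only potassium values dated before the outcome, and exclude the reading taken at the outcome admission.
2. Analyse hyperkalaemia as a time-updated exposure, by time-dependent Cox regression or by pooled logistic regression over intervals. Either also lets leavers be censored.
3. Report alongside it the association with baseline hyperkalaemia, which is measured before any outcome and so is free of both timing biases. It supplements goal d's question and does not replace it.
4. Keep hyperkalaemia admissions out of the outcome for this association and report them descriptively.

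The wording and programming are cheap; the cost is precision. The 27 expected new cases give 540 × ∫₀¹ 0.0513·e^(−0.0513t)·(1 − t) dt = 13.6 exposed person-years. That yields 13.6 × 0.0350 = 0.5 expected events at the overall risk, or 13.6 × 0.1054 = 1.4 at a 10% risk, with a 62% or 24% chance of none. Cases first found at month 12 add no exposed time. The new-onset part should therefore be labelled exploratory. Baseline exposure alone (60 against 540) has about 76% power for 10% against 2.5%, compared with the stated 80%.

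Death dates, hospitalisation data and follow-up blood tests are already planned. Appendix 1 is not shown, so confirm that the CRF records the dates of potassium values and of leaving. Reliance on clinically triggered tests before month 12 remains a limitation and should be stated.

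### Section 6 lets non-normality change how continuous variables are summarised but not how they are compared, which costs power in skewed variables and, if group SDs differ, distorts error in secondary comparisons.

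*Protocol*

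**What the plan says.** Protocol Section 6 gives two rules for continuous variables, one directly after the other. For description, the summary is "either the mean and the standard deviation or the median and interquartile range according them following or not a normal distribution". For comparison, "t-student test will be used for continuous variables", with chi-square for categorical ones. The second rule has no branch for variables that fail the normality condition in the first, and it does not say whether the variances are pooled.

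The same section estimates prevalence and cumulative incidence as proportions with 95% confidence intervals. The association between hyperkalaemia and outcomes is to be "adjusted using potential confounding factors by means of logistic regression models".

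The likely group sizes follow from Section 3.2. The sample size assumes "2.5% among the non-exposed and a 7:1 non-exposed/exposed ratio" and concludes that "73 exposed and 511 non-exposed patients should be included to have a 80% power to detect these differences with a 95% confidence level". The same section assumes 10% baseline prevalence in 600 patients and 5% incidence among those free of hyperkalaemia at baseline.

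**The concern.** The plan expects some variables to be non-normal and provides for this in the summary, but not in the test. A variable reported by its median would be compared through its mean. That is not a logical contradiction, but a test of means is inefficient when a distribution has a long tail.

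The second issue is the form of the test. Student's t-test in its usual form pools the two variances. With one group seven or more times the size of the other, the pooled variance is almost entirely that of the large group, whereas the uncertainty of the difference comes mostly from the small group. If the two spreads differ, the standard error is wrong, and a large total sample does not correct it.

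At stake is how reliably the study describes differences in continuous characteristics between groups, for example between patients with and without hyperkalaemia. Real differences in skewed variables could be missed, and p-values for variables with unequal spread could be too small or too large.

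**Working it through.** **Inputs from the protocol (Section 3.2).** Risks 10% and 2.5%, ratio 7:1, 80% power, 95% confidence, 600 patients, prevalence 10%, incidence 5%. SD ratios and skewness are assumptions, because the protocol gives none. Using hyperkalaemia status as the grouping is also an assumption, because Section 6 does not name the groups.

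**1. The plan's own figure.** Pooled-variance formula for two proportions without continuity correction:

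- Mean risk = (0.10 + 7 × 0.025)/8 = 0.034375.
- n = [1.96 √(0.034375 × 0.965625 × 8/7) + 0.842 √(0.10 × 0.90 + 0.025 × 0.975/7)]² / 0.075²
- n = (0.3817 + 0.2573)² / 0.005625 = 72.6, rounded up to 73. Then 7 × 73 = 511.

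The stated 73 and 511 are reproduced.

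**2. Group sizes implied by the protocol.**

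- Sample-size assumption: 73 vs 511 (7:1).
- Baseline: 10% of 600 gives 60 vs 540 (9:1).
- Incident cases: 5% of 540 gives 27 vs 513 (19:1).
- Hyperkalaemia at any time: 60 + 27 = 87 vs 513 (about 5.9:1).

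**3. Error of the pooled t-test at 73 vs 511, equal means, normal data.** Let r be the small-group SD divided by the large-group SD, with the large-group SD set to 1.

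- True variance of the difference: V = r²/73 + 1/511.
- Variance the pooled test uses, on average: P = [(72r² + 510)/582] × (1/73 + 1/511), where the last bracket is 0.015656.
- Approximate two-sided error: probability that a standard normal value exceeds 1.964/√(V/P) in absolute size.

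| r | V | P | √(V/P) | Error, formula | Error, simulation | Welch, simulation |
|---|---|---|---|---|---|---|
| 0.5 | 0.00538 | 0.01420 | 0.616 | 0.1% | 0.2% | 4.8% |
| 0.8 | 0.01072 | 0.01496 | 0.847 | 2.0% | 2.0% | 4.8% |
| 1 | 0.01566 | 0.01566 | 1.000 | 5.0% | 4.8% | 4.9% |
| 1.25 | 0.02336 | 0.01675 | 1.181 | 9.6% | 9.6% | 4.9% |
| 1.5 | 0.03278 | 0.01808 | 1.347 | 14.5% | 14.3% | 5.0% |
| 2 | 0.05675 | 0.02147 | 1.626 | 22.7% | 22.6% | 5.1% |

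Simulations used 20,000 runs per row. At 27 vs 513 the simulated error for r = 1.25, 1.5 and 2 is 11.0%, 17.1% and 28.0%.

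**4. Imbalance and skewness without a difference between groups.** With normal data and equal SDs, simulated error is 4.6% to 4.8% at all three pairs of sizes (73:511, 60:540, 27:513). With identical log-normal distributions in both groups (log SD 0.5 to 1.25), it is 4.8% to 5.5%. Only the split between tails becomes uneven, for example 3.7% and 1.1% at log SD 1.0 and 73 vs 511.

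**5. Power for skewed variables.** Log-normal data, log SD 1.0, 60 vs 540:

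| Log shift in small group | Student | Mann-Whitney |
|---|---|---|
| +0.4 | about 68% | 81% to 82% |
| −0.4 | about 53% | 81% to 82% |

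A test on the log scale keeps this power: 0.4/√(1/60 + 1/540) = 2.94, and 2.94 − 1.96 = 0.98, which corresponds to about 84%.

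The loss depends on the skew. At 73 vs 511, with the shift set so that a log-scale test has about 80% power, Student and Mann-Whitney give 77% vs 78% (upward shift) and 72% vs 78% (downward) at log SD 0.5. At log SD 1.0 they give 64% vs 78% and 51% vs 77%.

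**6. Welch alone is not enough.** On untransformed log-normal data (log SD 1.0, identical distributions), Welch's error is 7.6% at 73 vs 511 and 10.8% at 27 vs 513, against about 5% for Mann-Whitney.

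**The case against.** The strongest reply is that none of the specific goals needs this test. Hyperkalaemia, dose category, admission, death, diabetes and dichotomised renal function are all categorical, and Section 6 handles them with proportions and logistic regression. The t-test sits in a closing sentence on general methods. This stands, and it limits the importance of the point.

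A second reply is that test variants for secondary comparisons belong in a statistical analysis plan, and that naming Student's test does not by itself fix pooling. This stands in part: the error result is conditional on the pooled form. But Section 6 states a test for continuous variables immediately after providing for non-normal ones, so this is a stated choice rather than a detail left open.

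A third reply is that the SD ratios and skewness are invented. They are assumptions, which is why both directions are shown: a less variable small group makes the test conservative. With mild skew the power loss is small.

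A fourth reply is that Mann-Whitney is no cure for unequal spread. This also stands: with equal medians at 73 vs 511 it rejects about 7% to 12% of the time for SD ratios of 1.25 to 2.

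A reader might infer that the planned imbalance by itself misstates error. It does not; step 4 shows error near 5% unless the group SDs differ. Nor do all groupings reach 7:1: hyperkalaemia at any time gives about 5.9:1, and the protocol states no ratio for other groupings. A reader might also infer that these t-tests decide which factors count as related to hyperkalaemia or enter the adjusted model. Section 6 describes no such screening step.

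**Conclusion.** The point holds as a minor one. The comparison rule in Section 6 does not follow from its own description rule, and a better rule is available at almost no cost.

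The firmer consequence is lost power in clearly skewed variables: roughly 13 to 28 points at an assumed log SD of 1.0, small at 0.5. The conditional consequence is a wrong error rate, which requires both a pooled variance and group SDs that differ. At 73 vs 511 it then runs from about 0.2% to 22.6% for assumed SD ratios of 0.5 to 2. Actual sizes depend on variables whose spread and shape the protocol does not give.

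No prevalence or incidence estimate and no adjusted association with outcomes is affected.

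**What to change.** Replace the comparison rule for continuous variables in Section 6 with one that follows the description rule: variables described by mean and SD are compared with Welch's t-test; variables described by median and interquartile range are compared with Welch's t-test on the log scale where a log transform suits, and otherwise with the Mann-Whitney test.

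The cost is one sentence, with no extra data or patients. There are two drawbacks to accept. Mann-Whitney should be read as a comparison of distributions, not of means or medians, and it is not fully robust to unequal spread. A log-scale test compares geometric means, and the results should be reported that way.
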